labor, conduct statistical analysis on the efficacy, and evaluate whether the treatment plan achieves the desired therapeutic effect while reducing the occurrence of complications, thus providing a valid basis for the subsequent clinical treatment of missed abortion.

3. Research Design

Sample size calculation: Retrospective study of 400 cases

A prospective study of 180 cases

flow chart:

4. Research Content

This study is divided into two parts. The first part is a retrospective analysis to explore the differences in efficacy and fertility outcomes among patients with different treatment methods for missed abortion; the second part is a prospective study to explore the impact of different doses of estrogen combined with different treatment methods on the efficacy of treatment for missed abortion in early pregnancy.

Part I retrospective analysis collected data from patients with early pregnancy loss due to miscarriage who visited the Department of Gynecology at Xiangya Third Hospital of Central South University between January 2018 and March 2023. All patients had voluntarily accepted drug or surgical treatment and signed relevant treatment consent forms, and were exempted from signing informed consent forms regarding the data collection.

Part II, a prospective study, collected data from patients with early pregnancy loss due to miscarriage who visited the Department of Gynecology at Xiangya Third Hospital of Central South University between December 2023 and December 2024. All patients received either medication or surgical treatment at their own discretion. All participants were required to provide fully informed consent and sign an informed consent form.

Selection criteria:

① Age 18-40 years ; ② Diagnosed with early pregnancy missed abortion by imaging and laboratory examinations; ③ All indicators of routine examinations before treatment are within the normal range, and there are no serious systemic diseases; ④ No indication for emergency curettage ; ⑤ Good compliance, and follow-up observation as required (prospective study).

Exclusion criteria:

① Those with contraindications to medical abortion; ② Those allergic to estrogen or with contraindications to estrogen use; ③ Those unable to follow up according to the follow-up plan; ④ Those with thromboembolic diseases, known or suspected breast cancer, hormone-dependent tumors, etc.; ⑤ Those with vaginal bleeding exceeding the

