usual menstrual flow; ⑥ Those with serious heart, liver, or kidney diseases; ⑦ Those with serious internal or surgical diseases, malignant tumors, or mental illnesses who cannot cooperate.

4. Research Process

Grouping:

1. Retrospective analysis: Based on the different treatment methods for patients with early missed abortion, patients were divided into a drug treatment group and a surgical treatment group.

2. Prospective study: Patients with early missed abortions were grouped according to their own wishes to choose surgical or medical abortion, and to the use of different doses of estrogen before and after abortion treatment .

This study did not intervene in patient treatment; it only pre-designed and collected relevant data. No additional examinations or tests were performed on patients during the study, and all procedures were conducted according to standard clinical practice. After treatment, patients were divided into surgical and drug treatment groups based on their chosen treatment plans. Furthermore, based on the estrogen dosage chosen by the patients, they were divided into non-stimulatory estrogen, standard-dose estrogen, and high-dose estrogen groups. Data were then statistically analyzed.

Timing of treatment :

The following criteria are considered indicative of missed abortion in early pregnancy: Ultrasound diagnosis of missed abortion includes: ① Crown-rump length $\geq 7\text{mm}$, no fetal heartbeat detected. ② Average diameter of the gestational sac in the uterine cavity $\geq 25\text{mm}$, no embryo detected. ③ No yolk sac seen in the uterine cavity, and no embryo or fetal heartbeat detected after 2 weeks. ④ Yolk sac visible in the uterine cavity, and no fetal heartbeat detected after 11 days.

Treatment methods:

1. Retrospective Analysis: Patients diagnosed with early pregnancy loss at our hospital between January 2018 and March 2023 were included in this study. All patients were

informed of the available treatment options and associated risks before treatment and signed a treatment consent form. Patients were grouped according to their preferred treatment method: medication or surgery.

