(1) Drug treatment group: Patients clinically diagnosed with early pregnancy missed abortion who chose drug treatment were divided into groups according to their own wishes. Patients in the routine group were given mifepristone 50mg twice a day for two consecutive days on the first day, and misoprostol 600µg vaginally or 400µg sublingually on the third day. Patients in the experimental group were given estradiol valerate tablets 2mg twice a day for three days in addition to the treatment given to group A.

① The gestational sac is completely expelled, and the bleeding is less than menstrual flow. There are no contraindications to estrogen use. Patients can choose to take different doses of estrogen after medical abortion based on their own wishes. Group A (the standard group) does not require estrogen supplementation after medical abortion. Group B (the standard group) uses the standard dose of estrogen after medical abortion: 1 day after medical abortion (as above), oral estradiol valerate 1mg twice daily for 21 days, followed by dydrogesterone 10mg for the last 7 days. B i d , starting from day 5 of the next menstrual period, for a total of 2 cycles. Group C was the conventional group, using high-dose estrogen after medical abortion: 1 day after medical abortion (as above), estradiol valerate 2mg was administered orally . B i , 21 days, with dydrogesterone 10mg added for the last 7 days. B i d , starting from day 5 of the next menstrual period, for a total of 2 cycles. Group D (experimental group) did not receive estrogen supplementation after medical abortion. Group E (experimental group) received conventional doses of estrogen after medical abortion: 1 day after medical abortion (as above), estradiol valerate 1mg orally B i d, 21 days, followed by dydrogesterone 10mg for the last 7 days. B i d , starting from day 5 of the next menstrual period, for a total of 2 cycles. Group F was the experimental group, which received high-dose estrogen after medical abortion: 1 day after medical abortion (as above), estradiol valerate 2mg was administered orally . B i , 21 days, with dydrogesterone 10mg added for the last 7 days. B i d , starting from day 5 of the next menstrual period, for a total of 2 cycles. ② If the

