volume of distension fluid in and out; whether there is a decrease in blood oxygen saturation; whether complications such as uterine perforation, acute left heart failure, or gas embolism occur. Postoperative follow-up data : serum β -HCG, complete blood count, CRP, procalcitonin (not necessary), ultrasound to check for retained gestational tract, and if so, record the maximum diameter of the retained tract.

(5) Outpatient follow-up data 3 months after treatment : duration of vaginal bleeding after miscarriage, amount of bleeding, time of menstruation resumption , changes in menstrual flow , whether ultrasound indicates intrauterine adhesions, condition of endometrium, whether intrauterine adhesion surgery was performed, and intrauterine adhesion score.

(6) Pregnancy outcomes: Pregnancy rate after 1 year of trying to conceive (followed up every 6 months) ; spontaneous abortion rate, premature birth rate, full-term birth rate, stillbirth rate in subsequent pregnancies.

Follow-up data is used only for clinical efficacy evaluation.

6. Safety considerations

The data in this study are derived from clinical data and are absolutely safe. The use of estrogen for missed abortion is in accordance with routine clinical treatment, with the standard dose being 2 mg. 4 mg of estrogen is an off-standard dose, but numerous domestic and international studies have shown that high-dose estrogen for women of childbearing age without contraindications to estrogen use can effectively improve patients' clinical symptoms and has a high safety profile.

7. Statistical Analysis

using SPSS 26.0 software. Normally distributed measurement data were expressed as ($\bar{x} \pm s$), and t-tests were used for comparisons between two groups, while ANOVA was used for comparisons among multiple groups. Non- normally distributed measurement data were expressed as the median, and a nonparametric rank-sum test was used . Categorical data were analyzed using the χ^2 test or Fisher 's test. $P < 0.05$ was considered statistically significant.

8. Data integrity and quality assurance

Researchers should ensure that data is authentic, accurate, complete, and traceable, and should ensure the integrity of basic clinical research documents during retention, avoiding intentional or unintentional alteration or loss.

9. Ethical Statement

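### The no-estrogen groups also lack dydrogesterone, so for later outcomes only standard versus high dose bears on estrogen dose

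*Protocol*

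**What the plan says.** The Part II aim in Research Content is to "explore the impact of different doses of estrogen combined with different treatment methods on the efficacy" of treatment. Under Research Process, Grouping, the analysis factor is fixed by the estrogen dosage that patients chose: "they were divided into non-stimulatory estrogen, standard-dose estrogen, and high-dose estrogen groups".

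Treatment methods, part 2 (prospective study), gives the regimens:

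- **No post-treatment estrogen, drug arm:** "Group A (the standard group) does not require estrogen supplementation after medical abortion" and "Group D (experimental group) did not receive estrogen supplementation after medical abortion". Groups G and J are the surgical counterparts. No dydrogesterone is listed for any of the four.
- **Standard dose (Group B):** "oral estradiol valerate 1mg twice daily for 21 days, followed by dydrogesterone 10mg for the last 7 days". Groups E, H and K are the other standard-dose groups.
- **High dose (Group C):** estradiol valerate 2 mg for "21 days, with dydrogesterone 10mg added for the last 7 days". Groups F, I and L are the other high-dose groups.

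Section 7 (Statistical Analysis) provides t-tests for two groups, says that "ANOVA was used for comparisons among multiple groups", and gives rank-sum and chi-square or Fisher tests for other data, at P < 0.05. It does not mention dydrogesterone.

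**The concern.** The three levels are named and ordered as an estrogen-dose scale, but the step from none to standard changes two drugs at once. Only the step from standard to high changes estradiol with dydrogesterone present on both sides. A test across all three levels, or of none against either dose, mixes these two questions.

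At stake is what a positive result would be taken to mean. Research Background rests on a dose-dependent estrogen effect, and Safety considerations calls the 4 mg daily dose off-standard. A significant three-level result would naturally be read as support for dose, and so for the higher dose, although it could come entirely from having any combined cycle.

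**Working it through.** **1. Regimens side by side (post-treatment phase, as written).**

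| Level | Groups | Estradiol valerate | Dydrogesterone 10 mg |
|---|---|---|---|
| None | A, D, G, J | none | none listed |
| Standard | B, E, H, K | 1 mg twice daily, 21 days | listed in all four |
| High | C, F, I, L | 2 mg, 21 days (twice daily where legible) | listed in all four |

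None of the twelve groups A to L has a post-treatment estradiol cycle without dydrogesterone, or dydrogesterone without estradiol. The two drugs coincide completely in the none-versus-dose comparisons, so neither covariate adjustment nor a larger sample can separate them.

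**2. Which outcomes are exposed.** Where dydrogesterone is given in the last 7 of 21 days, it starts on day 21 − 7 + 1 = 15 of the cycle. Sac expulsion, operating time and intraoperative blood loss (Key Evaluation Indicators, items 3 and 4) are fixed before then. The 3-month bleeding, menstrual, endometrial and adhesion outcomes (item 5) and later pregnancy (item 6) are measured afterwards.

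**3. How often a three-level test would reject with no difference between doses.** The document gives 180 prospective cases but no effect size, SD, power or group sizes, so the 180 itself cannot be reproduced. Assumptions: an equal split, 180/3 = 60 per level; two-sided alpha 0.05; means (0, d, d) in SD units, so that standard equals high.

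The ANOVA noncentrality is λ = n Σ(μᵢ − μ̄)² with μ̄ = 2d/3, so λ = n d² (4/9 + 1/9 + 1/9) = (2/3) n d².

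- n = 60, d = 0.3: λ = 40 × 0.09 = 3.6. Against the critical F(2, 177) = 3.05, the rejection probability is 0.37.
- n = 60, d = 0.5: λ = 40 × 0.25 = 10. Rejection probability 0.81.
- n = 30 (one treatment arm only), d = 0.3 and 0.5: λ = 1.8 and 5. Rejection probability 0.20 and 0.49.
- d = 0: 0.05, as it should be.

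Unequal splits do not change the picture: 90/60/30 gives 0.41 and 0.86 at d = 0.3 and 0.5. For a binary outcome at 25%, 10% and 10% with 60 per level, λ = 60 × 0.015 / (0.15 × 0.85) = 7.06 on 2 df, and the chi-square test rejects in about 65%.

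**4. The contrast that does bear on dose.** In 20,000 simulated studies per scenario (60 per level; d = 0, 0.3, 0.5), standard versus high rejected in 4.8% to 5.2%. A linear trend over the three levels does not help: it rejected in 37% at d = 0.3 and 78% at d = 0.5.

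**The case against.** Several objections have force.

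- **The regimens are disclosed, and comparing whole regimens is legitimate.** This is so. The fault lies only in attributing the comparison to estrogen dose, which the level names and the stated aim invite.
- **Section 7 is generic.** It ties no test to this factor, already allows two-group tests, and a statistical analysis plan that is not shown may choose the contrasts. That stands for the choice of test. The exposure definition is not left open, however, and a later plan that kept these level names would inherit the problem.
- **The rejection rates are the power of an omnibus test when one group differs from two equal ones.** The same means would arise if estradiol worked and levelled off at the standard dose. This stands: the rates do not show that dydrogesterone has an effect, and the document gives no size for one.
- **The dose contrast has its own weaknesses.** Women choose their dose, so self-selection remains. In the drug arm, items ② and ③ of the treatment section give some women with incomplete or no expulsion estradiol 2 mg twice daily with no dydrogesterone listed at that stage, and a grouping by dosage could place them in the high level. In the surgical arm, dydrogesterone is worded differently across H, I, K and L: within the last 7 days for H and L, for a further 7 days for I and K, with a twice-daily frequency written only for K and L.

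Two stronger readings are tempting, and the text supports neither. A reader might infer that the control level takes no hormone at all, but D and J take estradiol before treatment. A reader might also infer that every outcome is affected, but those settled before the dydrogesterone days cannot be.

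**Conclusion.** The concern holds for outcomes measured after the dydrogesterone days. For these, none-versus-dose and three-level comparisons estimate the effect of combined estradiol/dydrogesterone cycles against no post-treatment hormone, and a significant result is not evidence for estrogen dose. This structural point needs no assumed effect size. It does rest on reading A, D, G and J as receiving no dydrogesterone: none is listed for them, although the text says only that they receive no estrogen supplementation.

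The 37% and 81% depend on an equal split of 180, shifts of 0.3 and 0.5 SD, and identical dose groups. They should not be quoted as the study's false-positive rate: they become false dose claims only if the three-level result is read as a dose effect. The problem is worth correcting because it changes what Part II can conclude, and the correction is cheap.

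**What to change.** In the Grouping text of section 4 and in section 7:

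1. Name the levels by post-treatment regimen as written: *no post-treatment hormone*, *estradiol 1 mg twice daily plus dydrogesterone*, *estradiol 2 mg twice daily plus dydrogesterone*. Record pre-treatment estradiol (D to F, J to L) as a separate factor. Keep women given estradiol under items ② and ③ of the drug-treatment text out of these levels, or identify them separately.
2. Base any estrogen-dose conclusion on one standard-versus-high contrast, pooled across treatment and pre-treatment strata and adjusted for them. First reconcile the dydrogesterone wording for H, I, K and L.
3. Report none versus any hormone as the effect of combined cycles, and draw no dose claim from the three-level test.

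The cost is wording and one planned contrast, with no change to treatment. The dose contrast uses only hormone users, about two thirds of Part II under an equal split. At 60 versus 60 its power is about 78% for a true 0.5 SD difference, and less once women under items ② and ③ are set aside. Pooling matters: with 180/12 = 15 per group, each separate within-stratum contrast would have about 26% power. Self-selection of dose remains a separate bias that this change does not remove.

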(1) Drug treatment group: Patients clinically diagnosed with early pregnancy missed abortion who chose drug treatment were divided into groups according to their own wishes. Patients in the routine group were given mifepristone 50mg twice a day for two consecutive days on the first day, and misoprostol 600µg vaginally or 400µg sublingually on the third day. Patients in the experimental group were given estradiol valerate tablets 2mg twice a day for three days in addition to the treatment given to group A.

① The gestational sac is completely expelled, and the bleeding is less than menstrual flow. There are no contraindications to estrogen use. Patients can choose to take different doses of estrogen after medical abortion based on their own wishes. Group A (the standard group) does not require estrogen supplementation after medical abortion. Group B (the standard group) uses the standard dose of estrogen after medical abortion: 1 day after medical abortion (as above), oral estradiol valerate 1mg twice daily for 21 days, followed by dydrogesterone 10mg for the last 7 days. B i d , starting from day 5 of the next menstrual period, for a total of 2 cycles. Group C was the conventional group, using high-dose estrogen after medical abortion: 1 day after medical abortion (as above), estradiol valerate 2mg was administered orally . B i , 21 days, with dydrogesterone 10mg added for the last 7 days. B i d , starting from day 5 of the next menstrual period, for a total of 2 cycles. Group D (experimental group) did not receive estrogen supplementation after medical abortion. Group E (experimental group) received conventional doses of estrogen after medical abortion: 1 day after medical abortion (as above), estradiol valerate 1mg orally B i d, 21 days, followed by dydrogesterone 10mg for the last 7 days. B i d , starting from day 5 of the next menstrual period, for a total of 2 cycles. Group F was the experimental group, which received high-dose estrogen after medical abortion: 1 day after medical abortion (as above), estradiol valerate 2mg was administered orally . B i , 21 days, with dydrogesterone 10mg added for the last 7 days. B i d , starting from day 5 of the next menstrual period, for a total of 2 cycles. ② If the

misoprostol is not expelled after medical abortion but there is no heavy vaginal bleeding, continue to administer 400µg of misoprostol sublingually or vaginally 3 hours later . The total daily dose (misoprostol) should not exceed 1800µg . If the misoprostol is still not expelled, surgical treatment may be temporarily withheld on the second day. High-dose estrogen 2mg B id can be combined to improve uterine contraction sensitivity. If the misoprostol is still not expelled, observation for one week or hysteroscopic surgery can be chosen.

③ If part of the pregnancy tissue is expelled without heavy bleeding and vaginal bleeding is less than menstrual flow, surgery may not be necessary initially. For those without contraindications, administer 2mg of estradiol valerate twice daily, check β-HCG weekly, and have a follow-up ultrasound every 2-3 weeks. If, during the waiting period, the pregnancy tissue is expelled and the remaining tissue is less than 5 mm in diameter , an artificial cycle will be initiated . After the next menstrual period, a follow-up ultrasound and HCG test will be performed, and the doctor will assess whether further surgery is needed. If heavy bleeding (more than twice the menstrual flow) occurs during the treatment, emergency hospitalization is required . If infection occurs during the treatment, emergency hospitalization is required, followed by aggressive anti-infection treatment and, depending on the circumstances, a curettage procedure may be necessary.

④ Heavy bleeding during medical abortion, with intensified uterine contractions (such as oxytocin) failing to expel the pregnancy tissue, and excessive bleeding. Examination reveals the pregnancy tissue is still within the uterine cavity, especially with no tissue impaction in the cervical canal (if present, it should be immediately removed with ovum forceps) . If bleeding significantly decreases after ovum forceps clamping , surgery is not performed immediately; instead, uterine contractions are intensified, and β-HCG is checked weekly. A follow-up ultrasound is performed in 3-4 weeks. If vaginal bleeding remains heavier than menstrual flow after clamping, emergency hysteroscopic-assisted or direct hysteroscopic surgery is necessary.

(2) Surgical treatment group: Patients clinically diagnosed with early pregnancy loss and choosing surgical treatment were grouped according to their own wishes. Group G

did not take estradiol valerate tablets before the curettage and underwent hysteroscopic curettage directly under ultrasound guidance . No estrogen supplementation was given after the procedure. Group H did not take estradiol valerate tablets before the curettage and underwent hysteroscopic curettage directly under ultrasound guidance . Starting from the first day after the procedure , estradiol valerate was administered orally , 1 mg twice daily for 21 days, and dydrogesterone 10 mg was added for the last 7 days. Two cycles of estradiol valerate were administered starting on day 5 of the next menstrual period . Group I did not take estradiol valerate tablets before the curettage and underwent hysteroscopic curettage directly under ultrasound guidance . From the first day after the procedure , estradiol valerate was administered orally , 2 mg twice daily for 21 days, followed by an additional 10 mg of dydrogesterone for the next 7 days. Two cycles of estradiol valerate were administered, starting on day 5 of the next menstrual period. Group J received 2 mg estradiol valerate orally three days prior to the procedure, followed by hysteroscopic curettage under ultrasound guidance on day 4. No estrogen supplementation was administered post-procedure. Group K received 2 mg estradiol valerate orally three days prior to the procedure , followed by hysteroscopic curettage under ultrasound guidance on day 4. Post-procedure , estradiol valerate was administered orally at 1 mg twice daily for 21 days, with an additional 10 mg dydrogesterone for the following 7 days. B i d , starting from day 5 of the next menstrual period, for a total of 2 cycles. Group L took estradiol valerate tablets orally for 3 consecutive days before the curettage , at a dose of 2mg B i d . On day 4, the curettage was performed under ultrasound guidance via hysteroscopy . From the first day after the procedure , estradiol valerate was taken orally , 2mg B i d, for 21 days, followed by dydrogesterone 10mg for the last 7 days. B i d , starting from the 5th day of the next menstrual period, for a total of 2 cycles. All surgically treated patients received an intrauterine injection of sodium hyaluronate gel after curettage to prevent intrauterine adhesions .

For all patients with missed abortions, treatment to promote uterine contraction after the expulsion of the pregnancy tissue includes: routine intravenous administration of uterotonic agents (oxytocin is commonly used , and ergonovine may be used if

necessary) ; and oral administration of uterotonic drugs (such as Wujia Shenghua capsules) for 2 weeks. Infection prevention: If signs of infection or high-risk factors for infection are present, antibiotics may be used as appropriate, and the type, route of administration, dosage, frequency, and duration of administration of antibiotics must be accurately recorded. Pathological examination: The pregnancy tissue expelled during the procedure is routinely sent for pathological examination; chromosomal analysis of the abortion tissue is performed based on the patient's preference.

End of treatment sign:

(1) A follow-up ultrasound showed no retained products of conception, and serum HCG levels returned to normal; (2) Patients with retained products of conception underwent clinical observation or curettage.

5. Key Evaluation Indicators

(1) Evaluation indicators before treatment: patient's age, time of consultation, gestational week of termination of pregnancy, symptoms, ultrasound findings of uterine size, gestational sac size and location, serum HCG level, parity , number of previous intrauterine procedures, and whether there are other intrauterine diseases before pregnancy (such as intrauterine adhesions, uterine septum , submucosal fibroids).

(2) Routine examination data after admission: routine vaginal discharge test, HPV/TCT, routine blood tests, liver and kidney function tests, electrolyte test , coagulation function test, thyroid function test, blood β -HCG test, anti-Müllerian hormone test, pre-transfusion examination, electrocardiogram, chest X-ray, uterine and bilateral adnexa 2-D/3-D color Doppler ultrasound and other related examinations.

(3) During drug treatment: the type and dosage of drugs taken, the time of expulsion of the gestational sac, the amount of vaginal bleeding, adverse drug reactions, etc.

(4) Surgical data: Date of surgery; depth of uterus; location and size of the gestational tract; operation time (from the start of the distension procedure to the withdrawal of the endoscope); amount of intraoperative blood loss; whether there is any retained gestational tract after surgery; clarity of the intraoperative field of vision;

volume of distension fluid in and out; whether there is a decrease in blood oxygen saturation; whether complications such as uterine perforation, acute left heart failure, or gas embolism occur. Postoperative follow-up data : serum β -HCG, complete blood count, CRP, procalcitonin (not necessary), ultrasound to check for retained gestational tract, and if so, record the maximum diameter of the retained tract.

(5) Outpatient follow-up data 3 months after treatment : duration of vaginal bleeding after miscarriage, amount of bleeding, time of menstruation resumption , changes in menstrual flow , whether ultrasound indicates intrauterine adhesions, condition of endometrium, whether intrauterine adhesion surgery was performed, and intrauterine adhesion score.

(6) Pregnancy outcomes: Pregnancy rate after 1 year of trying to conceive (followed up every 6 months) ; spontaneous abortion rate, premature birth rate, full-term birth rate, stillbirth rate in subsequent pregnancies.

Follow-up data is used only for clinical efficacy evaluation.

6. Safety considerations

The data in this study are derived from clinical data and are absolutely safe. The use of estrogen for missed abortion is in accordance with routine clinical treatment, with the standard dose being 2 mg. 4 mg of estrogen is an off-standard dose, but numerous domestic and international studies have shown that high-dose estrogen for women of childbearing age without contraindications to estrogen use can effectively improve patients' clinical symptoms and has a high safety profile.

7. Statistical Analysis

using SPSS 26.0 software. Normally distributed measurement data were expressed as ($\bar{x} \pm s$), and t-tests were used for comparisons between two groups, while ANOVA was used for comparisons among multiple groups. Non- normally distributed measurement data were expressed as the median, and a nonparametric rank-sum test was used . Categorical data were analyzed using the χ^2 test or Fisher 's test. $P < 0.05$ was considered statistically significant.

8. Data integrity and quality assurance

Researchers should ensure that data is authentic, accurate, complete, and traceable, and should ensure the integrity of basic clinical research documents during retention, avoiding intentional or unintentional alteration or loss.

9. Ethical Statement

